## 8. STUDY CALENDAR

	Pre-Study 0 – 42 days before surgery	Pre-OP 1 – 24 hours before surgery	Intra- OP	Post-OP/ Off Study d 14 – 28 days after surgery
Lymphoseek injection		X a		
IC-GREEN injection			X b	
Informed consent	X			
Demographics	X			
Medical history	X			
Physical exam	X			X
Vital signs	X			X
Height	X			
Weight	X			X
Performance status	X			
Adverse event evaluation		X	X	X
SPECT/CT imaging		X		
Laparoscopic gamma detection			X	
Laparoscopic near- infrared fluorescence detection			X	
B-HCG		X c		

a: Lymphoseek: 0.125 mCi x 4 each at 3, 6, 9, 12 o'clock (or 0.5 mCi +/- 20%) in the uterine cervix for same day surgery;  
0.5 mCi x 4 each at 3, 6, 9, 12 o'clock (or 2.0 mCi +/- 20%) in the uterine cervix for next day surgery  
b: IC-GREEN: injection of 0.5 mL each at 3, 6, 9, 12 o'clock in the uterine cervix after induction of anesthesia.  
c: Serum or urine pregnancy test (women of childbearing potential).  
d: Off-study evaluation at postop visit, i.e., 14 – 28 days after surgery, in person or remote telemedicine visit.

## 9. MEASUREMENTS

### 9.1 Primary Outcome

Bilateral SLN Detection (yes/no): For each subject, an assessment will be made of whether there was bilateral sentinel lymph node detection. A sentinel lymph node will be defined as being detected if it is detected on the pre-operative SPECT/CT imaging scan or intraoperatively using near-infrared imaging or the handheld gamma detection device. If at least one SLN is detected on each side, then this outcome will be considered a ‘Yes’.

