## 2. BACKGROUND

### 2.1 Study Disease

Endometrial cancer accounts for 50% of all gynecological malignancies in the US. The majority are diagnosed at an early stage. Although clinically locally confined, endometrial cancers may have microscopically spread to lymph nodes; therefore, International Federation of Gynecology and Obstetrics (FIGO) revised the endometrial cancer staging in 1988 to make it a surgical staging system and included a complete pelvic lymphadenectomy [1]. Despite the increased accuracy in staging, complete lymphadenectomy has not been shown in randomized trials to increase progression-free or overall survival [2, 3]. Instead, complete lymphadenectomy carries the risk of increased morbidity, including lymph edema and nerve damage. To reduce this morbidity while maintaining prognostic information, the concept of sentinel lymph node (SLN) sampling has been introduced [4, 5].

Various tracers have been used to identify the first draining lymph node, the sentinel lymph node, and assess for tumor involvement. In the thus-far largest multicenter prospective trial, detection rates for SLNs in minimally invasive surgery for endometrial cancer using Indocyanine Green alone have been reported as only 52% bilaterally and 86% overall [6]. Our own institutional data shows detection rates using Indocyanine Green of 69% and 88%, bilaterally and overall, respectively [7]. If a sentinel lymph node is detected, surgery is restricted to the removal of the SLN and a complete lymphadenectomy is avoided. If no lymph nodes are mapped, current guidelines recommend a complete lymphadenectomy on the side where no sentinel lymph node was detected. Thus, for 30-50% of patients the morbidity of a complete lymphadenectomy cannot be avoided.

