## **4. TREATMENT PLAN**

In this study, the patient will receive cervical injections of Lymphoseek 1 – 24 hours prior to surgery and subsequent SPECT/CT imaging preoperatively. Intraoperatively, following anesthesia induction, Indocyanine Green will be injected into the uterine cervix. Using near-infrared imaging, efferent lymphatic vessels and lymph nodes will be visualized and confirmed by detected radioactivity using a laparoscopic gamma counter. The preoperatively obtained SPECT/CT images will help guide the surgery. The laparoscopic gamma counter will confirm that sentinel lymph node tissue was removed by recording gamma counts before and after lymph node removal.

Subject participation in this study comprises the following:

- Screening**

- Screening begins after informed consent is obtained.
- The screening window is Day 1 to Day 42 after signing of informed consent.
- Screening assesses the subject's eligibility to participate as determined by inclusion/ exclusion criteria.

- Sentinel lymph node assessment**

- Preoperatively, 1 - 24 hrs prior to surgery, the patient will receive in the nuclear medicine suite of Stanford Hospital injections of 0.125 mCi or 0.5 mCi mL each Lymphoseek into the uterine cervix at 3, 6, 9, and 12 o'clock. Then, the patient will undergo SPECT/ CT imaging. Immediate and delayed static planar images will be obtained with and without a transmission source. SPECT-CT of the abdomen and pelvis will be obtained for further characterization. The imaging process will take approximately 1 hour.

- The patient will undergo minimally invasive endometrial cancer surgery. The SPECT/ CT images will be available for review to the surgeon prior to the start of the surgery.
- In the operating room, following anesthesia induction, the uterine cervix of the patient will be injected with about 2.0 mL total of Indocyanine Green. The surgery will start with the identification and dissection of sentinel lymph nodes.
- **Follow up (duration of the study)**
  - The patient will be observed preoperatively after Lymphoseek injection in the nuclear medicine suite and postoperatively in the recovery room for possible allergic reactions or any other adverse events.

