### 9.2 Secondary Outcome

(1) Overall detection (yes/no): For each subject, an assessment will be made of whether there was overall sentinel node detection. A sentinel lymph node will be defined as being detected if it is detected on the pre-operative SPECT/CT imaging scan or intraoperatively using near-infrared imaging or the handheld gamma detection device. If at least one SLN is detected (on any side), then this outcome will be considered a ‘Yes’.

(2) Location and number of SLNs detected by Lymphoseek: The location and number of sentinel lymph nodes detected by Lymphoseek will be assessed. A sentinel lymph node will be defined as being detected by Lymphoseek if it is detected using the pre-operative SPECT/CT imaging scan and/or intraoperatively using the gamma detection device.

(3) Location and number of SLNs detected by Indocyanine Green: The location and number of sentinel lymph nodes detected by Indocyanine Green will be assessed. A sentinel lymph node will be defined as being detected by Indocyanine Green if it is detected intraoperatively using near-infrared imaging only and not by the gamma detection device.

(4) Adverse events and severe adverse events will be monitored and reported.

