### **11.4.2. Analysis Plan**

The analysis for this study is primarily descriptive as the primary objective is to determine the detection rate of bilateral SLNs. The bilateral SLN detection rate will be calculated as the number of patients with bilateral SLN detection divided by the total number of patients. If the bilateral detection rate is at least 80%, we will deem this approach promising in detecting bilateral SLNs.

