### **11.5.2 Analysis Plan**

Descriptive statistics will be used to analyze the secondary outcomes. The overall detection rate of sentinel lymph nodes will be calculated as the number of patients with overall SLN detection divided by the total number of patients. To assess the safety of the concurrent use Lymphoseek and Indocyanine Green, we will calculate the number and rate of adverse events. We will describe the location and number of Lymphoseek-positive SLNs by method of detection (pre-operative or intraoperative). We will calculate the number of patients with SLNs found by Lymphoseek and by Indocyanine Green and conduct a McNemar's test (or mid- $p$  McNemar's test) to determine the concordance of Lymphoseek-positive and Indocyanine Green-positive sentinel lymph nodes.

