### **11.6.2 Sample size justification**

To address our primary objective, we plan to enroll 30 patients who have concurrent use of lymphoseek and indocyanine green. The sample size is based on a convenience sample from patients routinely followed in the Stanford gynecologic oncology clinic. With 30 participants and assuming a true bilateral detection rate of 80%, the probability of correctly concluding that our approach has an acceptable bilateral detection rate (i.e. 24 patients being detected with bilateral SLNs) is 61%. The probability of incorrectly concluding this (assuming that the true detection rate is 69% - the rate observed with current practice at Stanford) is low at 13%. We will deem the

approach used in this study promising if we observe a bilateral detection rate of at least 80%. The exact 95% confidence interval for the assumed bilateral detection rate of 80% is 61% to 92%.

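### A node seen only on pre-operative SPECT/CT counts towards the 80% rule, but the rule and its 13% false-call probability are set against 69%, a rate that can only come from mapping at surgery

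*Combined protocol and SAP*

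**What the plan says.** - **Endpoint.** Section 9.1 counts a node as detected "if it is detected on the pre-operative SPECT/CT imaging scan or intraoperatively using near-infrared imaging or the handheld gamma detection device". One such node on each side makes the patient a 'Yes'. The section does not ask for a node seen on the scan to be found at surgery.
- **Decision rule.** Section 11.4.2: "If the bilateral detection rate is at least 80%, we will deem this approach promising in detecting bilateral SLNs". Section 11.6.2 puts this at 24 of 30 patients, with a 61% chance of meeting it at a true rate of 80% and a 13% chance "assuming that the true detection rate is 69% - the rate observed with current practice at Stanford". Section 11.6.3 derives the 80% target from the same 69%.
- **Source of the 69%.** Section 2.1: "Our own institutional data shows detection rates using Indocyanine Green of 69"% bilaterally, and 88% overall.
- **When Indocyanine Green is read.** It is injected after anesthesia induction (sections 4 and 5.2.2). Section 9.2(3) defines a node as detected by it "if it is detected intraoperatively using near-infrared imaging only and not by the gamma detection device".
- **What an unmapped side means.** Section 2.1: "If no lymph nodes are mapped, current guidelines recommend a complete lymphadenectomy on the side where no sentinel lymph node was detected".
- **Use of the scan.** Section 4: "The SPECT/ CT images will be available for review to the surgeon prior to the start of the surgery".
- **Breakdown already planned.** Section 11.5.2 will describe the location and number of Lymphoseek-positive nodes "by method of detection (pre-operative or intraoperative").

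**The concern.** The three methods in section 9.1 are joined by 'or', so SPECT/CT alone is enough. The 69% benchmark could not have included any pre-operative finding, because with Indocyanine Green there is nothing to see before surgery. The scored endpoint is therefore broader than the rate it is judged against, and an extra route to 'Yes' can only raise the count.

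'Promising' is the only conclusion rule in this descriptive single-group feasibility study. As written, it can be met with no gain in bilateral mapping at surgery. By the protocol's own background, mapping at surgery is what spares a side a complete lymphadenectomy, and sections 2.1 and 2.3 give that as the reason for the study. The breakdown in section 11.5.2 leaves the primary count as it is, and no intraoperative-only bilateral rate is pre-specified.

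**Working it through.** **1. Reproduce the plan's figures.** Inputs from section 11.6.2: n = 30, cut-off 24, rates 0.69 and 0.80. Let X be the number of patients scored 'Yes'. By the exact binomial:

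- P(X ≥ 24 | 0.69) = 0.133, stated as 13%
- P(X ≥ 24 | 0.80) = 0.607, stated as 61%

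Both agree. The arithmetic is right; the question is whether 0.69 is the rate the section 9.1 endpoint would have if surgical mapping were no better than now.

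**2. Split the current-practice rate.** From section 2.1, both sides map in 69% and at least one side in 88%. If the two figures share a denominator (an assumption), one side maps in 88% − 69% = 19% and neither side in 100% − 88% = 12%.

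**3. Add the SPECT/CT route.** Hold surgical mapping at these rates. Let q be the fraction of surgically unmapped sides on which SPECT/CT shows a node. The documents do not give q. The scored bilateral rate is then:

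- sides independent: 0.69 + 0.19q + 0.12q²
- lower bound (no patient with neither side mapped is converted): 0.69 + 0.19q
- upper bound (both sides always converted together): 0.69 + 0.19q + 0.12q = 0.69 + 0.31q

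For example, at q = 10% with independent sides: 0.69 + 0.019 + 0.0012 = 0.7102, and P(X ≥ 24 | 0.7102) = 0.190.

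| q | Lower bound | Independent sides | Upper bound |
|---|---|---|---|
| 0% | 13% | 13% | 13% |
| 5% | 16% | 16% | 18% |
| 10% | 19% | 19% | 23% |
| 20% | 25% | 27% | 36% |
| 30% | 33% | 39% | 52% |
| 50% | 53% | 69% | 83% |

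Entries are P(X ≥ 24 of 30) with no improvement at surgery. With independent sides, the scored rate reaches 80% at q = 45%: 0.69 + 0.19 × 0.45 + 0.12 × 0.45² = 0.80.

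**4. The same effect in patients.** If SPECT/CT alone completes the second side in one patient, 23 surgical successes are enough, and P(X ≥ 23 | 0.69) = 0.243. With two such patients the bar is 22, and P(X ≥ 22 | 0.69) = 0.385. These figures avoid a model for q but take the number of such patients as given. In the independent-sides model, one expected conversion in 30 corresponds to q of about 16%, and two to about 30%.

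**The case against.** **The 13% is correct as stated.** It is conditional on a true rate of 69% for whatever is scored, and it reproduces. This stands as arithmetic. But section 11.6.2 presents 69% as current practice and 13% as the chance of a wrong conclusion. For the section 9.1 endpoint, no improvement at surgery does not mean a 69% rate.

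**SPECT/CT is part of the strategy under test, and the rule speaks only of detection.** Both are true. Section 2.3 values the scan for nodes in atypical locations. Its benefit is not lost under an intraoperative endpoint, since the surgeon sees the images first and any node they help to find at surgery still counts.

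**Large values of q are hard to defend.** A scan-only side needs a signal on SPECT/CT and then nothing on gamma probe or near-infrared imaging, within 24 hours, with a tracer that section 2.3 says stays bound for up to 30 hours. This is fair. At q = 5% the independent-sides model expects 30 × (0.19 × 0.05 + 0.12 × 0.05²) = 0.29 converted patients, and 13% becomes 16%. The rows at 30% and 50% show how the effect grows; they are not predictions.

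**The plan elsewhere places the outcome at surgery.** The synopsis and section 11.4.1 explain the absence of missing data by saying the outcome is established at the operation. That does not override section 9.1, but it sits badly with a scan-only 'Yes' and favours the change.

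**The study is small and descriptive.** Its stated 95% interval at 80% is 61% to 92%, which already includes 69%. This limits the weight of the label, but the plan still gives a threshold and error rates, and they should describe the endpoint that is scored.

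**Conclusion.** The concern holds. The primary endpoint has a pre-operative route to success that its 69% benchmark could not have had, so 13% is a floor for the chance of a 'promising' call when surgical mapping has not improved.

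The direction is certain; the size is not fixed by the documents. The chance is 16–18% if SPECT/CT alone shows a node on 5% of surgically unmapped sides, 19–23% at 10% and 25–36% at 20%. These ranges assume that 69% and 88% share a denominator and that surgical mapping is unchanged. The documents do not label the 69% as intraoperative; that follows from how and when Indocyanine Green is given and read. Gamma-probe detections also widen the endpoint relative to Indocyanine Green alone, but they are made at surgery and belong to the tested combination, so they are not part of this defect. The point should be fixed, and it does not call for a redesign.

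**What to change.** - In sections 9.1 and 11.4.2, and the matching text of the synopsis and section 11.6.2, apply the 80% (24 of 30) rule to bilateral detection made intraoperatively, by near-infrared imaging and/or gamma probe.
- Report the current composite including SPECT/CT as a secondary result, with the number of patients whose bilateral status depends on SPECT/CT alone.
- State how the 69% was defined. Do not add a node-removal requirement unless the 69% carried one.

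Keeping the composite as primary would be coherent only with a reference rate for that composite and recomputed error rates, and the documents give no such rate.

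**Cost.** Protocol wording only, provided the case report form records location by side for each method. Sections 9.2(2)–(3) and 11.5.2 already plan location, number and pre-operative or intraoperative method, but do not mention side explicitly, so this should be checked. N = 30 and the 61% and 13% figures stand. The downside is a possibly lower observed rate.

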### **11.4 Primary Analysis**

#### **11.4.1. Analysis Population**

The analysis population will include all patients who complete the study procedures specified above. We do not expect missing data or loss-to-follow up since the outcome is ascertained at the time of surgery. Patients who do not adhere to the study treatment plan of both injections, SPECT/CT and surgery will not be included in the analysis.

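### The primary endpoint counts a side as detected without requiring that a node be removed or confirmed as lymph node, so the bilateral rate judged against 80% can be overstated

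*Combined protocol and SAP*

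**What the plan says.** Section 9.1 (Primary Outcome) defines a sentinel lymph node as detected if "it is detected on the pre-operative SPECT/CT imaging scan or intraoperatively using near-infrared imaging or the handheld gamma detection device". The patient-level rule follows: "If at least one SLN is detected on each side, then this outcome will be considered a ‘Yes". Section 9.2(1) uses the same definition for overall detection.

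Section 11.4.1, like the synopsis, says that "the outcome is ascertained at the time of surgery" and gives this as the reason to expect no missing data. Section 11.4.2 takes the rate as "the number of patients with bilateral SLN detection divided by the total number of patients" and sets the decision rule: "If the bilateral detection rate is at least 80%, we will deem this approach promising in detecting bilateral SLNs". Section 11.6.2 bases this on 30 patients, a reference rate of 69% and a target of 80%.

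The nearest thing to a tissue check is in Section 4: "The laparoscopic gamma counter will confirm that sentinel lymph node tissue was removed by recording gamma counts before and after lymph node removal". Section 9.1 does not refer to it. Neither the study calendar (Section 8), the outcome measures (Section 9) nor the analysis plan (Section 11) has a pathology item.

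**The concern.** Section 2.1 explains why detection matters. The sentinel node is sought so that it can be assessed for tumor, and where none is found "current guidelines recommend a complete lymphadenectomy on the side where no sentinel lymph node was detected". Section 2.3 expects the combined approach to reduce the morbidity of complete lymphadenectomy. A side delivers that benefit only if a node is actually retrieved and can be examined.

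The rule in 9.1 does not ask for this, and two kinds of side pass without it:

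- **Scan-only sides.** A node is called on the preoperative SPECT/CT, but nothing is found or removed on that side. Because the three methods are joined by *or*, the scan alone is enough.
- **Empty specimens.** Tissue is removed as a sentinel node and turns out not to be lymph node.

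Both count as success in the only endpoint that carries a decision rule. The margin at the cut-off is thin: 24/30 is 80.0% and 23/30 is 76.7%, so one such patient can change the conclusion.

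**Working it through.** **1. The plan's own figures.** Inputs from 11.4.2 and 11.6.2: n = 30; promising if the observed rate is at least 80%, that is at least 24 of 30; reference 69%; target 80%. Exact binomial:

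- P(X ≥ 24 | n = 30, p = 0.80) = 0.607 (stated 61%)
- P(X ≥ 24 | n = 30, p = 0.69) = 0.133 (stated 13%)
- Exact 95% interval for 24/30: 61.4% to 92.3% (stated 61% to 92%)

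All reproduce. The arithmetic is sound; the question is what is being counted.

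**2. Direction.** Every side with a removed, confirmed node that was located by one of the three methods also meets the rule in 9.1. The reverse need not hold. So the recorded rate is at least the node-confirmed rate, and it is higher whenever a patient is counted on a side that yields no node.

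**3. Does the gamma count close the gap?** Counts before and after removal show that radioactivity left the field. They do not show that the tissue was nodal, they cannot verify a site positive for Indocyanine Green only, and 9.1 does not make them a condition of success.

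**4. Size, under two assumptions.**

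- *Assumption A:* the 69% is a node-confirmed rate. Sections 2.1, 11.6.2 and 11.6.3 do not say how it was scored.
- *Assumption B:* a side counted as detected yields no nodal tissue with probability e, independently between sides. The documents give no value. Here e refers to the whole side: every node called there, by any method, is either not retrieved or not nodal.

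Then recorded rate = confirmed rate / (1 − e)². With a confirmed rate of 0.69:

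| e per side | (1 − e)² | Recorded rate | P(X ≥ 24 of 30) |
|---|---|---|---|
| 0 | 1.0000 | 69.0% | 13% |
| 0.5% | 0.9900 | 69.7% | 15% |
| 1% | 0.9801 | 70.4% | 17% |
| 2% | 0.9604 | 71.8% | 22% |
| 5% | 0.9025 | 76.5% | 42% |
| 8% | 0.8464 | 81.5% | 69% |

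A recorded 80% corresponds to a confirmed 69%, which is no gain, when (1 − e)² = 0.69/0.80 = 0.8625, so e = 1 − √0.8625 = 7.1%. Positive dependence between a patient's two sides would make these effects smaller.

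**5. If assumption A fails.** If the 69% was itself scored on intraoperative mapping without tissue confirmation, empty Indocyanine Green specimens sit in both rates and that part largely cancels. Section 2.1 ties the 69% to Indocyanine Green, so sides counted only on SPECT/CT or the gamma probe would still be added on the new side of the comparison alone.

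**The case against.** The best defense is that this is a choice of estimand. The objective is a detection rate in a feasibility study whose analysis is mainly descriptive, and in Section 2.1 what triggers lymphadenectomy on a side is that no node was detected there. An intraoperative detection rate follows that decision closely, and node-confirmed retrieval is a different, stricter endpoint. This stands in part: signal detection is worth reporting. It does not cover a side called only on the preoperative scan, and a side with no nodal tissue gives nothing to assess for tumor.

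A reader might also infer more than the documents support:

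- *That a fluorescent channel counts as success.* It does not. Section 9.1 makes a sentinel lymph node the thing detected, and Section 4 names lymphatic vessels separately from nodes. The gap is that nothing verifies the call that something is a node.
- *That the rate is overstated as a matter of fact.* The documents show only that it can be. If every counted side yields a node, the two rates agree.
- *That the true false-positive risk is 22% to 69% rather than 13%.* Those figures need both assumptions above. At e of 0.5% to 1% the risk is 15% to 17%, and nothing in the documents favors the larger values of e.

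**Conclusion.** The point holds as a weakness in the endpoint definition. The rule in 9.1 is complete as written and requires neither removal nor nodal tissue, and no other section adds such a requirement. The direction of any bias is certain: the recorded rate cannot fall below the node-confirmed rate. Its size is not known. The range from 15% to 69% for declaring the approach promising, against the stated 13%, is conditional on a node-confirmed 69%, on an assumed e between 0.5% and 8%, and on independent sides. The change should be made because it concerns the sole primary endpoint, the decision turns on single patients, and the remedy is cheap.

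**What to change.** - In 9.1 and 9.2(1), score a side as detected only if at least one sentinel node located by any of the three methods was removed from that side at surgery and is reported as lymph node tissue on the pathology report.
- Keep the present signal-only rate as a secondary outcome, so no information is lost.
- Add a pathology field per side to the CRF.
- Amend the statement in the synopsis and 11.4.1 that places ascertainment at surgery, together with the no-missing-data expectation built on it, and say how a missing pathology report is scored.
- State how the 69% was defined, and compare it with the rate from this trial scored the same way. If the 69% and 80% are node-confirmed rates, the stated 13% and 61% stand unchanged. If the 69% is not node-confirmed, setting it against a confirmed rate would bias the comparison against the new approach.

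Cost: revised wording in these sections and one CRF item, assuming that pathology of sentinel nodes is routine. Sample size and surgical procedures do not change. The downside is a headline rate that may be slightly lower and an outcome known only after pathology.
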